We decided not to include extended release naltrexone (XR-NTX), because its cost currently is prohibitive and because, unlike XR-NTX, methadone is widely available in community treatment programs throughout Baltimore and elsewhere in the US for continuing care post-release. We decided to include a detoxification arm as a comparison because virtually all jails in the US (including in Baltimore) use detoxification as their "treatment as usual." In doing so we will be affording a less distressing detoxification regimen (using methadone rather than clonidine) for the treatment-as-usual condition in Baltimore City (and elsewhere) because clonidine is considered inferior to methadone for symptom relief.⁹⁸ We decided that combining PN with detoxification was impractical because newly-released opioid-dependent detainees not on opioid agonists at the time of release, unlike those in the IM+PN and IM alone conditions who will be on medication and referred to one of 3 particular programs, would be very difficult for the PNers to track, engage, and link to the many different types of treatment programs available in Baltimore City. Finally, to maximize human subject protection and to exceed the services typically offered in jails, all study participants will be provided with enhanced treatment-as-usual (ETAU) including substance use, overdose and HIV prevention information, as well as Baltimore's Behavioral Health Systems central telephone intake and assessment line, to reduce their risk of relapse (see **Human Subjects**).

2. Study Sites

Baltimore City Pretrial and Detention Services. The Baltimore City Pretrial and Detention Services is a Division of Maryland's Department of Public Safety and Correctional Services (DPSCS). It operates three facilities on its downtown campus in Baltimore City including Central Booking, where all arrestees in Baltimore City are brought by police and the Men's and Women's Detention Centers (the sites of the proposed study). Annually, there are 57,925 arrestees (not unduplicated) that pass through Central Booking for processing and transfer to the Men's and Women's Detention Centers. The Men's Detention Center has 2,684 beds and the Women's Detention Center has 861 beds. The average length of stay in the Detention Centers is 42 days and individuals who are sentenced for more than a few months are transferred to prisons elsewhere.

3. Participants in the Proposed Research

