After providing informed consent and completing a baseline assessment (see **Measures**, below), participants will receive information about HIV prevention, overdose prevention, and substance use and then will be randomly assigned to 1 of the 3 study conditions: 1) IM with PN; 2) IM alone; or, 3) enhanced treatment-as-usual (ETAU), including Methadone Detoxification. Participants will be assigned to conditions using a random permutation procedure, such that, within gender, for each block of 3, 6, or 9 participants, $\frac{1}{3}$ rd will be assigned at random to the IM with PN Condition, $\frac{1}{3}$ rd to the IM alone condition, and $\frac{1}{3}$ rd to the ETAU condition, ensuring that both male and female participants have an equal chance of being assigned to each of the 3 conditions. [Random block sizes will be used in order to thwart any attempt by an interested observer, such as a staff member, to deduce the random assignment procedure.] Sealed opaque envelopes will be prepared for the project RA at each detention center based on this random permutation procedure. The RA will open the

designated envelope and inform the participant to which one of the conditions s/he has been assigned. Only the project manager and PI will have access to the random assignment table.

6. Study Conditions

6.a. Methadone Detoxification (Enhanced Treatment-as-Usual)

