Follow-up and Attrition: Consistent with the parent study^{25,26} and our prior research with opioid-dependent patients^{23,24} we will collect detailed locator information, including cell phone numbers (for calls or texts), contact information for relatives and peers, and names and addresses of participants' "hang-outs." We will also, with permission of the participant, collect email addresses and social media contact information (e.g., facebook; Twitter) in order to contact the participant. When unable to contact participants via phone, the RAs will track the participants in the community through our successful and robust procedures for participant tracking. Thus, we expect to obtain follow-up rates of about 90%, consistent with our previous studies in Baltimore City with out-of-treatment opioid dependent individuals^{23,24,105} and the parent study.^{25,26} The PI and his staff have located over 90% of participants at 10-month follow-up for the first study of Interim Methadone, and at 12 months in both the parent study, and in the RCT of methadone for prisoners.³⁹

Measures: Figure 1 shows a schedule of the measures corresponding to each study aim.

Figure 1. Data Collection Schedule and Measures by Aim

Measures	Baseline	Follow-up
Aims 1-2: To compare IM + Patient Navigation v. IM alone v. Methadone Detoxification (Enhanced Treatment-as-Usual) on: treatment entry and retention, illicit opioids and cocaine use, DSM-5 criteria for opioid and cocaine use disorders; HIV-risk behaviors, criminal activity, arrest, and incarceration.		
Treatment Entry (self-report from Methadone Treatment Exposure form))		1 month
Enrolled in Treatment (self-report from Methadone Treatment Exposure form)*		3, 6, & 12-month
Illicit Opioid and Cocaine Use (ASI and urine drug testing)	◆	1,3, 6, & 12-month
DSM-V Criteria of opioid and cocaine use disorder (modified WMH CIDI)	◆	3- 6, and 12-month
Criminal Behavior (ASI)	◆	1,3, 6, & 12-month
Arrests and Incarcerations: Self report and criminal justice records	◆	12-month
HIV Risk Behavior (RAB)	◆	6, & 12-month
Overdose AE Form		1,3, 6, & 12-month
Methadone Treatment Exposure Questionnaire		1,3, 6, & 12-month
Quality of Life (WHOQOL-BREF)	◆	1,3, 6, & 12-month
Aim 3: To conduct a cost-benefit analysis of the relative costs of the three study Conditions		
Economic Form 90 (Health care utilization)	◆	3, 6, & 12-month
Substance Abuse Services Cost Analysis Program (SASCAP)		†

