Arrest and incarceration (Criminal Justice Records)	◆	12-months only

* Participants transitioning directly to other community MMPs or buprenorphine treatment will be considered still in treatment.

† Consistent with prior research, the SASCAP will be administered once during the treatment phase.

Participants will be paid \$30 for follow-up interviews (regardless of whether they are conducted in the community or during a re-incarceration) and will provide consent for research staff to check hospital and arrest records. Participants who are interviewed for follow-up during a re-incarceration will have the option to receive their \$30 deposited into their jail or prison account or to have a money order mailed to a designated person. They will not be paid for the baseline interview conducted in jail to avoid the perception of coercion.

Longer-term follow-ups: Participants will be asked (using a consent form addendum) if they'd be willing to have a 24-month follow-up interview for which they would be paid \$40. The 24-month interviews will include the same assessments as the 12-month interviews described above. In addition they will be asked if the research team could contact them beyond the 24-month follow-up for further informed consent for even longer-term follow-up interviews.

Measures for Aim 1 and 2:

Entry into Treatment: within the first 30 days of release from jail will be obtained from patient self-report from the Methadone Treatment Exposure form.

Enrollment in Treatment: will also be obtained from self-report on the Methadone Treatment Exposure form.

Addiction Severity Index (ASI): assesses patient functioning through a 30-45 minute interview covering 7 key domains over the past 30 days including drug and alcohol use, legal, medical, psychiatric and employment status, family functioning and social relations.¹⁰⁶ Composite scores and items from each domain will be investigated (with particular emphasis on drug use and legal scores and items).

Urine Drug Testing: Urine samples will be collected by project staff at 1, 3, 6, and 12 months post-baseline and tested by an approved rapid drug test cup for opiates, methadone, buprenorphine, cocaine, and benzodiazepines. Results will be used for research purposes only and will not be shared with clinic staff.

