Explanatory Variables. The predictor variables in all statistical models can be categorized as either Treatment Variables, Moderator Variables, or Control Variables.

Treatment Variables: There will be a single treatment variable with three conditions: Intervention Condition [IM+PN v. IM Alone v. Methadone Detoxification (ETAU)].

Moderator Variables: There will be a single moderator variable: Participant Gender.

Control Variables: Three additional predictor variables – participant age, prior methadone maintenance treatment (yes v. no), and self-reported cocaine use at baseline – will be included as “main effects” in all analyses in order to examine for potential differences in treatment outcome as a function of these three variables. (In the parent study: 56% had never previously been in MM treatment; and, self-reported cocaine use at baseline predicted lower treatment retention at 6 months).

Time: Finally, the “repeated factor” in the statistical analysis of all outcome variables measured repeatedly will be assessment Time point, which will allow for the evaluation of both *differential course and impact* of the interventions as a function of the “between-subjects” Treatment Condition factor. (For information regarding which outcome variables are measured at what assessment time points, see **Figure 1. Outcomes and Measures by Aim and Measures**, above).

Planned Contrasts: It is possible to construct two orthogonal, single-degree-of-freedom, planned contrasts that directly test **Hypothesis 1A** and **1B**, respectively. Contrast 1A will compare the two IM treatment conditions (IM+PN and IM Alone, pooled) to the Methadone Detoxification condition. Thus, this comparison directly addresses the question of the differential effectiveness of some form of IM treatment in comparison to a ‘minimally sufficient’ treatment-as-usual (methadone detoxification). Contrast 1B will compare the IM+PN condition to the IM alone condition. Hence, this comparison directly addresses the question of the relative

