Consenting opioid-dependent detainee participants will be interviewed four times, at study entry during detention (baseline) and at 1,3, 6, and 12 months post-release while in the community. Participants will receive \$30 for each of the three assessments in the community for a possible total of \$120. No payment will be provided for the baseline interview in the detention center because this could be considered coercive given the financial constraints of incarcerated individuals. However, participants who are re-incarcerated may participate in follow-up interviews, in which case, they will have the option of receiving their \$30 payment deposited in their jail or prison account or to have it mailed to a person of their choice. The 32 participants who participate in the qualitative interviews will receive an additional \$30 per each of two interviews for a potential total of an additional \$60. Follow-up qualitative interviews will not be conducted for re-incarcerated participants because it will not be possible to bring a recorder into the correctional institutions. In addition, participants providing a signed informed consent addendum will be interviewed at 24-months following enrollment and receive \$40 for completing that interview.

The patient navigators will not receive payment for their interview because they will be interviewed during regular working hours.

The following instruments will be used to obtain information from the 300 opioid-dependent participants:

Addiction Severity Index (ASI): assesses patient functioning through a 30 -45 minute interview covering 7 key domains over the past 30 days including drug and alcohol use, legal, medical, psychiatric and employment status, family functioning and social relations.¹⁰⁶

Urine Drug Testing: Urine samples will be collected by project staff at 3 and 12 months post-baseline and tested by an approved rapid drug test cup for opiates, methadone, buprenorphine, cocaine, and benzodiazepines. These results will be used for research purposes only and will not be shared with clinic staff.

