They will be informed that if they are assigned to the interim methadone + patient navigator condition, a study staff member serving as patient navigator will meet with them in the detention center to assess potential barriers to their entry into methadone treatment upon release. They will be told that the navigator will be available to them for three months after release to help them enter and remain in treatment. These services may include help: getting a bus pass, arranging childcare, and referring their significant others to drug abuse treatment. Navigators will also be available to provide advocacy for them with their drug treatment program.

Participants will be informed that they will receive a series of assessments at study entry and at 1, 3, 6, and 12 months post-release. A urine sample will be collected during the assessments in the community. They will be told that all of their urine test data and responses to the assessment questions will be confidential and will not effect their treatment at the detention center or in the community. The limits of confidentiality will be explained including threats of harm to self or others, child or elder abuse, or certain communicable diseases (e.g., tuberculosis). They will be informed that their study involvement requires their consent for the research staff to obtain their methadone treatment data from his/her detention center methadone program record, treatment information from the methadone program in the community that they attend as well as admission, discharge dates from any other public drug treatment programs attended during the course of the study, and their arrest and incarceration records from the criminal justice system.

In addition, participants who provide a signed informed consent addendum will be interviewed at 24-months after enrollment using the same interview and urine collection approach as for the 12-month interview.

Potential risks

Risks of substance abuse. Risks of opioid and/or other substance abuse include: overdose death, infections including but not limited to endocarditis, soft tissue infection, hepatitis, kidney infection, HIV infection, seizure, stroke, and trauma from motor vehicle, machinery, or violence.

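### For urine drug tests, the only repeated-outcome test the plan names (Contrast X Time) has follow-up levels only, so a sustained treatment benefit is detected at about alpha; no averaged follow-up contrast is pre-specified

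*Combined protocol and SAP*

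**What the plan says.** **Schedule.** In Figure 1 (Research Interviews) one row, "Illicit Opioid and Cocaine Use (ASI and urine drug testing", covers both instruments. It has a baseline mark and follow-up at 1, 3, 6 and 12 months. Under Analyses for Aims 1 and 2, the Time paragraph points back to that figure: "For information regarding which outcome variables are measured at what assessment time points, see".

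The text that schedules urine directly gives three accounts:

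- Measures for Aim 1 and 2, Urine Drug Testing: "Urine samples will be collected by project staff at 1, 3, 6, and 12 months post-baseline".
- Human Subjects, Research Information: "Urine samples will be collected by project staff at 3 and 12 months post-baseline".
- Human Subjects, Participant Recruitment: "A urine sample will be collected during the assessments in the community". The optional 24-month visit follows suit, "using the same interview and urine collection approach as for the 12-month interview".

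None of them schedules a sample at the in-jail baseline visit. That visit comes before allocation (Random Assignment: "After providing informed consent and completing a baseline assessment").

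**Analysis.** Outcome Variables lists opioid and cocaine urine results among the dichotomous outcomes, treated as binomial. The method is a generalized linear mixed model. Planned Contrasts says the contrasts can be examined in interaction with Time, and as a simple effect at a visit if a Contrast X Time interaction is significant. The Power section is written for Contrast X Time. It treats the contrast itself as the effect of interest only for retention and for arrest and incarceration, which have no Time factor.

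**The concern.** The other drug-use measures, the ASI and the CIDI, are interviews, so urine is the only objective one. With follow-up levels only, Contrast X Time asks whether the gap between arms changes from one follow-up visit to another. It does not ask whether there is a gap. Hypothesis 1A predicts lower illicit use under interim methadone. If that benefit is in place at the first follow-up and persists, the interaction is null. The condition in Planned Contrasts then also closes the visit-by-visit comparisons. For Hypothesis 1B the protocol itself allows that effects may fade by 6 and 12 months; in that case a significant interaction would mainly register the fading. What is at stake is whether the main question for urine has a pre-specified test at all.

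**Working it through.** **1. The plan's own power figure.** The Power section gives f² = .048, N = 270, alpha = .01, power .9 for Contrast X Time. The set-correlation form is u = kX·kY, v = m·s + 1 − u/2, λ = f²(u + v + 1). With set sizes 2 and 4 (my inference; none are given), u = 8, s = 2, m = 270 − 4.5 = 265.5 and v = 531 + 1 − 4 = 528. Then λ = .048 × 537 = 25.8 and power is .901. The figure can be reproduced, but only with inferred set sizes. A single-df contrast crossed with 3 df of Time gives .69. The GLIMMIX figure of .81 cannot be rebuilt, because its rates and covariances are not given. Either way, these are powers for an interaction.

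**2. Inputs for the check.** From the documents: 100 per arm, about 90% follow-up (hence 180 v 90 for Contrast 1A) and alpha .01. Sidedness is not stated; I take two-sided. Assumed: 50% v 65% or 45% v 65% positive at each of four follow-up visits, and a random-intercept SD of 1.8. By numerical integration that SD implies a within-person correlation of about .35 between visits.

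**3. Contrast X Time, follow-up only.** At every visit the log-odds difference is δ = logit(.65) − logit(.50) = .619 − 0 = .619. For 45% it is .619 + .201 = .820. The interaction tests whether δ₃ − δ₁, δ₆ − δ₁ and δ₁₂ − δ₁ are all zero. All are zero, so the noncentrality is 0 and the rejection probability equals alpha, .01. Simulation gave .01 to .02. The result does not depend on the size of δ, and it is the same with two visits (3 and 12 months).

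**4. Contrast averaged over four follow-up visits.** The variance per arm is p(1 − p)(1 + 3ρ)/(4n), and (1 + 3 × .35)/4 = .5125.

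- 50% v 65%: .25 × .5125/180 + .2275 × .5125/90 = .000712 + .001295 = .002007. SE = .0448, z = .15/.0448 = 3.35, power = Φ(3.35 − 2.576) = .78.
- 45% v 65%: .000705 + .001295 = .002000. SE = .0447, z = .20/.0447 = 4.47, power = Φ(1.90) = .97.

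Simulation gave about .77 and .96.

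**5. Would a baseline sample rescue the interaction?** Assume 90% positive in both arms at baseline. The baseline log-odds ratio then has SE √[1/(180 × .09) + 1/(90 × .09)] = √(.0617 + .1235) = .43. That is large beside an effect of .619 or .820, and the interaction spends 4 df. Simulated power on the log-odds scale is about .08 and .17; a large-sample version of the same Wald test gives .07 and .14. On the risk-difference scale the figures are about .5 and .82, but the plan's binomial mixed model, discussed as logistic regression, works on log-odds.

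**6. Sensitivity.** Assume 60% positive in the comparison arm, 10 to 20 points lower in the other, and correlation .3 to .5.

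| Test | 1A (180 v 90) | 1B (90 v 90) |
|---|---|---|
| Contrast X Time, follow-up only | .01 | .01 |
| Contrast X Time with 90% baseline | .03 to .23 | .03 to .15 |
| Average of 4 visits | .27 to .97 | .19 to .90 |
| Average of 4 visits, 15 points | .64 to .78 | .49 to .63 |
| Average of 3 and 12 months, 15 points | .54 to .62 | .40 to .47 |

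The last row shows why the disagreement over the 1- and 6-month samples has to be settled first.

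**The case against.** The plan's language is permissive. The Time paragraph says both the course and the effect of the interventions are to be evaluated, and Planned Contrasts says the contrasts *can* be examined in the ways listed. The guiding principle commits to confidence intervals and effect sizes, and a mixed model readily yields an overall contrast. This stands as far as it goes: a competent analyst could report the right comparison. But no section names it as the test for repeated outcomes, and the one route to visit-level effects is conditional on the interaction.

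The Figure 1 row is labelled by construct, and the ASI does have a baseline value, so the mark may be meant for the ASI alone. I accept this. Taken by itself, the row is a matter of clarity.

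A reader might infer that urine is taken only after release. Only the Participant Recruitment text places collection in the community. The other two places count from baseline, and since "The average length of stay in the Detention Centers is 42 days", a 1-month sample could fall in jail. What the documents support is narrower: outside the shared row, none of them schedules a baseline sample.

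**Conclusion.** The point holds for urine outcomes and for the test the plan names. With follow-up levels only, a steady arm difference is detected by Contrast X Time at about alpha = .01, whatever its size. Under the assumed rates, the averaged contrast has power of about .77 (50% v 65%) or .96 (45% v 65%). The null-interaction result needs only a difference that is constant on the model's scale. The power contrast rests on assumed rates, correlation and two-sided alpha, and step 6 of the working gives the range.

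Two stronger readings are tempting, and the documents do not support them. One is that the missing baseline sample is the cause and should be added. Allocation is random, so the follow-up comparison is valid without it, and with it the interaction test stays weak. The other is that the trial cannot detect a sustained benefit or will report none. The data would support the comparison; what is missing is its pre-specification.

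**What to change.** 1. Reconcile the urine schedule across Figure 1, Urine Drug Testing under Measures, and the two Human Subjects sections, including whether 1- and 6-month samples are collected.
2. Split the Figure 1 row so that the baseline mark applies to the ASI only.
3. For urine outcomes, pre-specify Contrasts 1A and 1B as the arm difference averaged over the reconciled follow-up visits. Report visit-level estimates and confidence intervals whether or not Contrast X Time is significant. Baseline ASI days of use may be added as a covariate.
4. Keep Contrast X Time for urine as a secondary test of course.
5. State in the Power section that the Contrast X Time power does not apply to the urine treatment effect.

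The cost is a corrected figure row, a reconciled schedule and a few sentences in the analysis and power text. No new samples or visits are needed.

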Methadone detoxification will be provided by the medical team at the jail. All methadone provided in the jail is directly administered by the nursing staff. Medical staff will discontinue treatment as usual (clonidine, etc) for participants assigned to methadone detoxification and will begin typically with up to 30 mg methadone on the first day, which can be increased by 5 mg per day up to a maximum of 40 mg in response to the daily administered COWS scores. Once a stable dose has been achieved at which the participant is comfortable, it will be decreased by 5 mg per day. It is anticipated that detoxification will last an average of 7-10 days. This Enhanced Treatment-as-Usual Condition will also include substance use information and substance use treatment referral, HIV prevention information, and overdose prevention information. The research assistant will provide the participants assigned to this Condition with the contact information for the Baltimore City behavioral health authority's (Baltimore Behavioral Health Systems) telephone assessment and referral help line (see **Letter of Support** from Baltimore Substance Abuse Systems). This help line provides telephone screening and referral to a wide range of publicly-funded drug abuse treatment and harm minimization services (overdose prevention and needle exchange), and 12-step meetings in Baltimore. In summary, this condition will be superior to the detoxification-as-usual afforded to arrestees because participants will receive detoxification with methadone rather than clonidine and other non-opioids, and they will also receive the central intake and referral number for substance use treatment and harm minimization services in Baltimore, as well as information about overdose prevention, HIV risk prevention, and substance use.

6.b. Interim Methadone Maintenance without Patient Navigation (IM alone)

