passes), housing challenges, and fluctuating motivation. Gender-specific issues will be addressed, such as obtaining child care and referrals to treatment for drug using significant others. PNers will arrange to meet the participant at the selected MMP for the first visit to maximize the likelihood of keeping the appointment. PNers will remain with the participant during the intake process to assist in communication with the MMP if necessary and to advocate for the participant. They will also facilitate keeping treatment appointments through reminders, coaching, and if necessary, meeting the participant either at the MMP or in the community to accompany them. The PNers will call participants who miss appointments to determine what happened and to facilitate another appointment or referral. PNers will seek out participants if they cannot be reached by phone (much the same way that our research staff now does for follow-up interviews using extensive locator information).

Once a participant is enrolled in treatment, the PNer will assist them (if necessary) in gaining an ID card and will provide them with bus or train tokens for the first few weeks until a reduced fare bus pass can be obtained. If necessary, navigators will assist the participant in complying with the instructions provided by the clinic staff in completing required documentation to obtain Medicaid or Maryland's state health benefits that will pay the clinic for treatment, whether MM or some other modality. Limited funds will be available for the PNers to obtain bus tokens, and to pay for ID cards and other needed low-cost services.

It is anticipated that the PNers will meet with the participants weekly during the first month, and about every other week (or more) during the second and third months, as needed. Phone calls will be made in between appointments or used as reminders or to seek the participant out if appointments are missed.¹⁰³ As needed, the PNers will go into the community to find the participant at their home or usual hangouts to try to reengage them following the procedures that we use successfully in tracking this population for research follow-ups. The PNers will enter in an excel database and written progress notes all of their participant-related activities including all attempts at contacting participants, PN services delivered, site of PN services, referrals made, and community services received.

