Methadone Dose: Higher methadone maintenance doses in jail have been shown to be related to higher rates of treatment entry following release from incarceration²² and improved retention rates in community-based treatment.⁴⁶ As such, methadone dose will be recorded at release from the Detention Center and at each follow-up to permit an examination of the relationship between methadone dose and outcomes by treatment Conditions.

Overdose AE Form. This brief 12 item questionnaire was devised for the present study to examine the number and characteristics and responses to any non-lethal overdoses between study visits.

Methadone Treatment Exposure Questionnaire. This brief 7 item questionnaire was devised for the present study to examine methadone treatment status, anticipated length of sojourn in methadone treatment, and reasons for leaving treatment (if applicable).

Measures for Aim 3:

Economic Form 90: The Economic Form 90 survey has been modified for our ongoing research in MMPs and used successfully to collect data on participant outcomes and economic outcomes before, during, and after treatment. This instrument is useful to supplement the ASI whose time frame for follow-up interviews is restricted to the past 30 days for items such as arrest and hospitalization. The Economic Form 90 is a modified version of the Form 90 family of instruments that was originally designed to collect alcohol use and economic outcome data for alcohol treatment studies.^{112,113} It will be used to collect data on residential drug treatment, outpatient, and emergency room health care utilization; criminal behavior including number of arrests, severity of offense, and nights incarcerated. Also collected will be labor market information including employment status, current wage, frequency of work, and amount of money received beyond paid employment (e.g., Social Security) and off-the-books earnings.

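### Treatment entry and enrolment are scored from a form described only in methadone terms, so a first treatment with buprenorphine or another modality has no documented route to being counted and Contrast 1A may favour IM

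*Combined protocol and SAP*

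**What the plan says.** **Entry.** Under Measures for Aim 1 and 2, entry "within the first 30 days of release from jail will be obtained from patient self-report from the Methadone Treatment Exposure form". Figure 1 lists it at 1 month as "Treatment Entry (self-report from Methadone Treatment Exposure form", with no footnote.

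**Enrolment.** Figure 1 lists it at 3, 6 and 12 months as "Enrolled in Treatment (self-report from Methadone Treatment Exposure form". This row carries the asterisk, whose footnote says: "Participants transitioning directly to other community MMPs or buprenorphine treatment will be considered still in treatment".

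**The form.** The Measures section describes it in one sentence: "This brief 7 item questionnaire was devised for the present study to examine methadone treatment status", followed by the expected stay in methadone and the reasons for leaving. The seven items are not reproduced.

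**The target.** Aim 1(a) and Hypotheses 1A and 1B speak of treatment entry and retention without naming a modality. The rationale for 1A refers to community-based treatment. Section 6.c directs navigation at entry into community drug abuse treatment.

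**The routes into treatment.** Section 6.d and Participant Recruitment give both IM arms assured admission to a participating methadone program if they arrive within 3 days of release. Section 6.a gives ETAU participants a telephone line, of which it says: "This help line provides telephone screening and referral to a wide range of publicly-funded drug abuse treatment and harm minimization services". Section 1 (Study Design Issues) expects detainees who leave without an agonist to be spread over many kinds of program.

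**The concern.** The hypotheses are about treatment, but the instrument is about methadone. Someone who starts with buprenorphine, residential care or outpatient care has no stated way to register as having entered.

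For enrolment, the footnote admits buprenorphine by one route only. Two participants on buprenorphine at month 3 can be scored differently: one who moved directly from a methadone program is credited, and one who began on buprenorphine is not covered. The Background section notes that switching to buprenorphine is possible in Baltimore, so the case is foreseeable.

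The route into treatment depends on randomisation. If non-methadone entry is more common in ETAU, entries are lost mainly from the control arm and Contrast 1A (pooled IM v ETAU) overstates the benefit of IM on the first-listed Aim 1 outcome. The entry and retention components of Hypothesis 3b reuse the same scores.

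**Working it through.** **1. What the documents supply.** There is no plan figure to reproduce. The Power section gives α = .01, N = 300 and N = 270 after attrition, but no rate or power for treatment entry. The rationale for 1B quotes entry of 14% to 50%, but only for entry into methadone maintenance among inmates started on it in jail. No ETAU rate and no non-methadone share appear anywhere. Everything in steps 3 to 5 is therefore assumption.

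**2. How the rule treats each path, as written.**

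| Path after release | Entry, 1 month | Enrolment, 3, 6, 12 months |
|---|---|---|
| Enters a methadone program and stays | Counted | Counted |
| Enters a methadone program, moves directly to buprenorphine | Counted (methadone entry) | Counted (footnote) |
| First treatment is buprenorphine | No stated route | No stated route |
| First treatment is residential or outpatient care | No stated route | No stated route |

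**3. Effect on Contrast 1A.** Let p be true entry into any treatment and s the share of entrants who use non-methadone care. Methadone-only scoring records p(1 − s), so

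recorded difference − true difference = p_ETAU·s_ETAU − p_IM·s_IM.

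Assume p = 30% in both groups and s_IM = 5%. IM is recorded as 30 × 0.95 = 28.5%.

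| s_ETAU | ETAU recorded | False IM advantage | Chance of a significant result for IM |
|---|---|---|---|
| 10% | 27.0% | 1.5 points | about .01 |
| 25% | 22.5% | 6.0 points | about .06 |
| 50% | 15.0% | 13.5 points | about .45 |

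The last column is a simple two-proportion normal approximation, 180 v 90 (270 in equal arms), two-sided α = .01; the plan does not state sidedness. For the bottom row:

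- pooled rate = (180 × .285 + 90 × .15)/270 = .24
- null standard error = √[.24 × .76 × (1/180 + 1/90)] = .0551
- alternative standard error = √[.285 × .715/180 + .15 × .85/90] = .0505
- power = Φ[(.135 − 2.576 × .0551)/.0505] = Φ(−.14) ≈ .45

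This is not the planned mixed model and serves only for scale.

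**4. Direction of the 1A bias.**

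- True entry 50% v 30%, s_IM = 5%: the true 20 points read as 47.5 − 22.5 = 25.0 (s_ETAU = 25%) or 47.5 − 15.0 = 32.5 (s_ETAU = 50%).
- True entry 50% v 10%, s_ETAU = 25%, s_IM = 5%: 47.5 − 7.5 = 40.0, equal to the truth. The losses cancel.
- True entry 30% in both, s_ETAU = 0, s_IM = 5%: 28.5 − 30.0 = −1.5, against IM.

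A bias toward IM needs p_ETAU·s_ETAU to exceed p_IM·s_IM. The referral routes make that plausible; no figure in the documents establishes it.

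**5. Effect on Contrast 1B.** Assume entry of 50% in IM alone and 65% in IM+PN, with a 5% non-methadone share in IM alone (recorded 47.5%). The true 15 points read as:

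- IM+PN share 0%: 65.0 − 47.5 = 17.5
- 10%: 58.5 − 47.5 = 11.0
- 20%: 52.0 − 47.5 = 4.5

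The change runs from +2.5 to −10.5 points, so the sign is not fixed.

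**The case against.** **Methadone entry may be the intended outcome.** The trial tests interim methadone with transfer to methadone programs, and the rationale for 1B cites entry into methadone maintenance. On that reading nothing is misclassified and the hypotheses merely need tighter wording. This is the strongest objection and it stands in part, because the plan never defines the outcome. It does not fit the footnote, which counts buprenorphine as treatment for some participants.

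**A reader might infer that the plan scores other treatment as non-entry.** It does not say so, and the form's items are not shown. What the text supports is the absence of any stated route to being counted.

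**A reader might infer that the arms are scored by different rules.** They are not. Form, visits and footnote apply to every participant; an ETAU participant who enters a methadone program and moves directly to buprenorphine is covered. The telephone line is also given to all arms. Only the likely impact differs.

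**A reader might infer that navigation is penalised in 1B.** The phrase "that will pay the clinic for treatment, whether MM or some other modality" comes from a sentence about help with insurance paperwork and does not show navigators steering people away from methadone. Both IM arms are routed to the same four programs.

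**Other data exist.** Economic Form 90 covers residential drug treatment and outpatient care at 3, 6 and 12 months under Aim 3; the urine panel includes buprenorphine; consent covers "admission, discharge dates from any other public drug treatment programs attended during the course of the study". These make repair easier, but none is tied to entry or enrolment. Form 90 is not given at 1 month, and a positive urine screen shows exposure rather than enrolment.

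**Conclusion.** The point holds as a gap between hypothesis and measurement. Both outcomes rest solely on a form described in methadone terms, buprenorphine is credited only as a direct transition and only for enrolment, and a first treatment of another kind has no documented route to being counted. Contrast 1A may be biased toward IM, because assured methadone admission belongs to the IM arms alone.

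The size is unknown. The 1.5 to 13.5 points rest on assumed equal true entry of 30%, a 5% non-methadone share in IM and an ETAU share of 10% to 50%. It would be wrong to add the whole ETAU loss to the 1A difference, since missed entries in IM offset part of it.

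The documents do not support a directional claim for Contrast 1B. Nor is Hypothesis 3b affected as a whole: its drug use, DSM-5, HIV risk and criminal justice components do not depend on these scores.

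**What to change.** Before analysis:

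1. State which treatments count, and apply that one rule to entry (30 days) and enrolment (3, 6, 12 months) in all three arms.
2. Replace the Figure 1 footnote so that starting on buprenorphine counts the same as a direct transfer to it.
3. Add one item at each visit on the type and program of any drug treatment, or use the admission and discharge dates already covered by consent. That consent refers to public programs, so the item gives wider coverage; for visits already completed, the dates are the available route.
4. Report methadone entry, methadone-or-buprenorphine entry and any-treatment entry separately, so that a reader holding either view of the outcome can find the relevant contrast.

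The cost is one questionnaire item and one definition. The IM v ETAU difference on entry may look somewhat smaller.
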